8. PRIOR AND CONCOMITANT THERAPIES

Current medications and any medications taken within 30 days prior to the start of the study (Baseline) will be recorded as prior/concomitant medications with the dose (in source documents only) and corresponding indication. The medications to be recorded include prescription, OTC medications, and vitamins, minerals, and dietary supplements being taken for a therapeutic indication. Vitamins and mineral supplements are permitted at dosages considered by the investigator as reasonable for maintaining good health and will not be recorded on the electronic case report forms (eCRFs). All concomitant medications will be coded with the current version of the WHO Drug Dictionary.

Any changes in concomitant medications and/or procedures/therapies during the study must be recorded. The reason for any changes in concomitant medications and/or procedures/therapies should be reported and should reflect either a baseline medical condition documented in the medical history or in conjunction with an AE.

8.1 Prohibited Medications or Therapies

Subjects must not use the medications or procedures in the timeframe noted below.

Within 24 hours of study visits during the study:

- Antipruritics, including antihistamines.

Within 2 weeks prior to Baseline and during the study:

- Topical retinoids (e.g., tazarotene, adapalene, and tretinoin) on the face;
- Topical anti-acne treatments including, but not limited to, OTC acne cleansers, soaps, washes or treatments, benzoyl peroxide, antibiotics, azelaic acid, dapsone, sulfa based products, corticosteroids, and salicylic acid on the face;
- Topical steroids on the face;
- Topical antibiotics on the face;
- Topical anti-inflammatory agents on the face;
- Neuromuscular blocking agents such as botulinum toxin type A (e.g., BOTOX, DYSPORT) at any body site.

Within 30 days prior to Baseline and during the study:

- Investigational drugs, devices, or biologics.

Within 4 weeks prior to Baseline and during the study:

- Cryodestruction or chemodestruction, dermabrasion, photodynamic therapy including other light-based and laser therapies, acne surgery, intralesional steroids, or x-ray therapy on the face;
- Systemic corticosteroids (including intramuscular, intra-articular, and intralesional injections) for any indication;
- Systemic antibiotics¹¹ for any indication or other systemic anti-acne medications;
- Androgen receptor blockers (e.g., spironolactone, flutamide);
- Anti-inflammatory agents or immunosuppressive drugs.

Within 6 months prior to Baseline and during the study:

- Systemic retinoid therapy (e.g., isotretinoin);
- Vitamin A supplements (greater than 10,000 units per day).

¹¹ Contact the Medical Monitor if a subject requires concomitant antibiotic therapy.

During the study, the following are prohibited:

- Any other topical or systemic therapy, which may materially affect the subject's acne, in the investigator's opinion;
- Exposure to excessive sunlight or artificial tanning devices.

8.2 Allowed Medications or Therapies

Contraception for WOCBP is required per Inclusion Criterion #8 (see [Section 5.1.1](#)). Vitamins and mineral supplements are permitted at dosages considered by the investigator as reasonable for maintaining good health and will not be recorded in the eCRFs.

Subjects must be on a consistent skin care regimen for at least 4 weeks prior to Visit 1/Baseline and must not alter the regimen for the entire study. NOTE: Subjects who change from using a medicated acne cleanser that contains benzoyl peroxide, salicylic acid, etc. to using a bland non-medicated/non-acne cleanser prior to Visit 1/Baseline will only be required to have used the new non-acne cleanser for at least 2 weeks in order to establish a stable skin care regimen. Allowed skin care products include any type or brand of make-up, cleanser, non-medicated facial product, or hair product (e.g., Clinique foundation, Cetaphil soap, shampoo, hair gel, hairspray, mousse). General skin/hair care products (e.g., shampoo, hairspray, Cetaphil soap) and minimal use of non-medicated facial products and make-up (e.g., light powder, light foundation, lip stick, mascara, sunscreen) is permitted after test article application and a 10-minute dry-down period, provided that the subject has been using the products for at least 4 weeks prior to Visit 1/Baseline. Changes in the use of type or brand of eyeliner for use on the eyes, lipstick, and/or mascara for the eyelashes are allowed prior to and during the study since these products do not involve facial areas typically affected by acne and thus, do not materially impact the Treatment Area. These and other allowed skin care products do not need to be recorded in the eCRFs. With respect to sunscreen, if sunscreen is not part of the subject's stable skin care regimen, sunscreen may be used in the Treatment Area for significant sun exposure events (e.g., out on a boat all day); however, such use of sunscreen should be listed as a concomitant medication or therapy and recorded in the eCRFs.

Therapies (medication and non-medication therapies) not restricted by the protocol may be used during the study for the treatment or prevention of disease or to maintain good health.

Non-prohibited chronic therapies being used at Visit 1/Baseline may be continued, but must be recorded.

Intranasal steroids as well as inhaled (puffer) or ophthalmic steroid preparations are allowed.

Reasonable use of OTC medications such as NSAIDs (e.g., aspirin, ibuprofen) or analgesics or antipyretics (e.g., acetaminophen) for relief of headache, muscle ache, etc. is allowed during the study and must be recorded.

9. STUDY PROCEDURES

Specific activities for each study visit are listed below.

9.1 Visit 1 (Day 1): Screening/Baseline

At Screening, the investigator or qualified designee will:

- Obtain a signed, written informed consent/assent.
- Record subject demographics.
- Review inclusion/exclusion (I/E) criteria and confirm subject eligibility.
- Record medical history.
- Record prior and/or concomitant medications and procedures/therapies.
- Have subject complete washout from any prohibited medications, if necessary.

If the subject requires washout from previous medications, the remaining activities will be performed after washout is complete as a separate Baseline Visit.

- If the washout requires longer than 45 days, re-consent/assent should occur.
- Reconfirm I/E criteria and subject eligibility.
- Perform a dermatological exam.
- Measure vital signs (including temperature, systolic and diastolic blood pressure, heart rate, and respiration rate) and height and weight (see [Section 10.3.3](#)).
- Perform a UPT for all WOCBP. The results must be negative for the subject to be enrolled.
- Perform clinical evaluations: IGA (see [Section 10.1](#)) and acne lesion counts (see [Section 10.2](#)).
- Assess LSRs (see [Section 10.3.2](#)).
- Perform standardized photography of the face (see [Section 11](#)).
- Randomize the subject and assign the subject kit according to the IWRS.
- Document Test Article Accountability. Weigh test article prior to dispensing to subject and record baseline weight.
- Demonstrate how to apply test article using the non-medicated samples provided to the site and have subject apply the non-medicated sample in the clinic under staff supervision to ensure proper application. Instruct the subject to apply the first dose on the evening of the Baseline Visit.
- Review and dispense a Subject Instruction Sheet (see [Appendix 1](#)).
- Dispense the Subject Diary and provide completion instructions (see [Appendix 2](#)).
- Review allowed skin care products per [Section 8.2](#).
- Schedule a follow-up telephone call (Visit 2) and in clinic follow-up (Visit 3).

9.2 Visit 2 (Day 15 ± 3): Follow-Up Telephone Call

At this phone visit, the investigator or qualified designee will:

- Query the subject about any changes in health status or any AEs since the last visit. Document in the AE section of the eCRF, as appropriate. NOTE: If severe tolerability issues or a material AE concern of any type are noted, the subject may be scheduled for an in-office visit at the investigator's discretion.
- Record any changes in the subject's concomitant medications and procedures/therapies.
- Review the Subject Diary and test article compliance.
- Remind the subject to continue to apply test article twice daily to their entire face, once in the morning and once in the evening, until the next clinic visit and to bring all bottles (used and unused) of test article with him/her to the next clinic visit.
- Confirm the next scheduled visit and remind the subject or parent/legal guardian (if applicable) not to apply test article or other products to the face within 4 hours prior to the next appointment.
- Review allowed skin care products per [Section 8.2](#).
- Inquire if the subject has any other questions or needs; in the event the subject is having any issues with the test article or material health concerns, the investigator will determine if an unscheduled visit (see [Section 9.5](#)) or other measures are required.
- Call the day prior to the next scheduled visit to remind subjects not to apply test article or other products to the face within 4 hours of the next visit.

9.3 Visits 3 and 4 (Week 4/Day 29 ± 3 and Week 8/Day 57 ± 4): Follow-Up

At this visit, the investigator or qualified designee will:

- Query the subject about any changes in health status since the last visit. Document in the AE section of the eCRF, as appropriate.
- Record any changes in the subject's concomitant medications and procedures/therapies.
- Perform clinical evaluations: IGA (see [Section 10.1](#)) and acne lesion counts (see [Section 10.2](#)).
- Assess LSRs (see [Section 10.3.2](#)).
- Document Test Article Accountability. The subject's new and used test article will be weighed and re-dispensed as necessary.
- Collect, review, and distribute the Subject Diary as necessary.
- Review test article compliance. Test article application will be demonstrated if deemed necessary.
- Remind the subject to continue to apply test article twice daily to their entire face, once in the morning and once in the evening, until the next clinic visit and to bring all bottles (used and unused) of test article with him/her to the next clinic visit.

- Schedule the next visit and remind the subject or parent/legal guardian (if applicable) not to apply test article or other products to the face within 4 hours prior to the next appointment.
- Review allowed skin care products per [Section 8.2](#).
- Call the day prior to the next scheduled visit to remind subjects not to apply test article or other products to the face within 4 hours of the next visit.

9.4 Visit 5 (Week 12/Day 85 ± 4): End of Study or Early Termination

At this visit, the investigator or qualified designee will:

- Query the subject about any changes in health status or any AEs since the last visit. Document in the AE section of the eCRF, as appropriate.
- Record any changes in the subject's concomitant medications and procedures/therapies.
- Perform a UPT for all WOCBP.
- Perform clinical evaluations: IGA (see [Section 10.1](#)) and acne lesion counts (see [Section 10.2](#)).
- Assess LSRs (see [Section 10.3.2](#)).
- Document Test Article Accountability. Weigh and collect all test articles.
- Collect and review the Subject Diary and determine test article compliance.
- The subject will exit the study.

9.5 Unscheduled Visit

An unscheduled in-office follow-up visit may be completed at the discretion of the investigator for subjects with tolerability issues or a material AE concern.

At this visit, the investigator or qualified designee will:

- Query the subject about any changes in health status or any AEs since the last visit. Document in the AE section of the eCRF, as appropriate.
- Record any changes in the subject's concomitant medications and procedures/therapies.
- Assess LSRs, if applicable (see [Section 10.3.2](#)).
- Review the Subject Diary and test article compliance.
- Remind the subject to continue to apply test article twice daily, once in the morning and once in the evening, until the next clinic visit and to bring all bottles (used and unused) of test article with him/her to the next clinic visit.
- Confirm the next scheduled visit and remind the subject or parent/legal guardian (if applicable) not to apply test article or other products to the face within 4 hours prior to the next appointment.
- Review allowed skin care products per [Section 8.2](#).
- Call the day prior to the next scheduled visit to remind subjects not to apply test article or other products to the face within 4 hours of the next visit.

10. CLINICAL EVALUATIONS

The following clinical evaluations will be performed according to the schedules indicated during the study. The same investigator should complete the evaluations for a given subject throughout the study. If this becomes impossible a sub-investigator with overlapping experience with the subject and the study should complete the evaluations.

10.1 Investigator's Global Assessment

The IGA score is a static evaluation of the overall severity or “average” degree of severity of a subject's disease by the investigator or qualified designee, taking into account all of the subject's facial acne lesions as the subject appears on the day of the evaluation. The investigator should NOT refer to any other assessments to assist with this evaluation and should complete the IGA score prior to performing lesion counts. This evaluation is NOT a comparison with the IGA at any other visit or a mathematical calculation based on counts of individual lesion types. Overall severity of acne will be assessed using a five-point scale from 0=Clear to 4=Severe. Subjects must have an IGA score of 2 (mild), 3 (moderate), or 4 (severe) at Baseline.

Grade	Description
0	Clear skin with no inflammatory or non-inflammatory lesions.
1	Almost clear; rare non-inflammatory lesions with no more than a few small inflammatory lesions.
2	Mild severity; greater than Grade 1; some non-inflammatory lesions with no more than a few inflammatory lesions (papules/pustules only, no nodular lesions).
3	Moderate severity; greater than Grade 2; up to many non-inflammatory lesions and may have some inflammatory lesions, but no more than one small nodular lesion.
4	Severe; greater than Grade 3; up to many non-inflammatory lesions and may have some inflammatory lesions, but no more than a few nodular lesions.

10.2 Acne Lesion Counts

The number of non-inflammatory lesions (open and closed comedones), inflammatory lesions (papules and pustules), and nodulocystic lesions (nodules and cysts) on the face (including those present on the nose) will be counted. Subjects must have a minimum of 25 but no more than 100 non-inflammatory lesions AND a minimum of 20 but no more than 70 inflammatory lesions AND ≤ 2 nodulocystic lesions on the face at Baseline.

The entire face, vertically from the hairline to mandible rim and horizontally from ear to ear (not including any lesions on or in the ear), including the nose, will be examined for lesions defined as follows:

Non-inflammatory lesions:

- Comedones: open (blackheads) and closed (whiteheads).

Inflammatory lesions:

- Papules: raised inflammatory lesions with no visible purulent material.
- Pustules: raised inflammatory lesions with visible purulent material.

Nodulocystic lesions:

- Nodules and cysts: any circumscribed, inflammatory masses greater or equal to 5 mm in diameter with or without cystic changes.

10.3 Safety Evaluations

10.3.1 Adverse Events

All reported or observed AEs will be recorded. At each visit, subjects will also be questioned specifically about the status of any ongoing AEs. Untoward events that occur prior to the first dose of test article will be captured in the Medical History section of the eCRF unless they are related to a study-specific procedure. See [Section 14](#) for details on Adverse Event Reporting.

10.3.2 Local Skin Reactions

At each visit, LSRs (erythema, edema, scaling/dryness, stinging/burning, pruritus, erosion, and pain) will be assessed. Erythema, edema, scaling/dryness, and erosion will be assessed by the investigator and stinging/burning, pain, and pruritus will be assessed by the subject. Assessments will be made using a 4-point ordinal scale where 0=absent, 1=mild (slight, barely perceptible), 2=moderate (distinct presence), and 3=severe (marked, intense). Only LSRs that require medical intervention (e.g., prescription medication), require withholding or discontinuation of the application of the test article, or extend 2 cm beyond the Treatment Area will be documented as AEs. Any LSR that are not listed above will be recorded as an AE.

10.3.3 Vital Signs

Vital signs including temperature, systolic and diastolic blood pressure, heart rate, and respiration rate will be measured at Visit 1/Baseline. Assessments will be made after the subject has rested in a seated position for at least 5 minutes. Height and weight will also be measured at Visit 1/Baseline.

10.3.4 Urine Pregnancy Tests

A UPT will be performed at Visit 1/Baseline and at Visit 5/Week 12/EOS for WOCBP.

10.3.5 Concomitant Medications and Concurrent Procedures/Therapies

Concomitant medications and concurrent procedures/therapies will be reviewed at all visits and any changes will be recorded.

11. PHOTOGRAPHY

Photography documentation is required in this study so to participate in the study subjects must consent to photographs. Photographs taken as part of this study will be used to document the subject's baseline disease, AEs, or other findings during the study. The site will be provided with suggested guidelines to assist them in taking standardized photographs of the face in 3 views (front, right, and left [45 degrees oblique for right and left]) at Baseline. All photographs taken as part of this study are for informational purposes only and are not to assist in grading or for any other assessment. Photographs will be compiled and reviewed and may be used to evaluate investigator/grader training needs, but no formal assessments will be performed.

Note: Subjects who decline to have photographs taken during the conduct of study after Baseline may continue to participate in the study. If a subject initially consents to photographs, then declines further photography as/if required, the Sponsor may use the photographs taken under consent for the purposes noted above.

Additional details regarding photographic methods, uploading and labeling photos etc. will be provided in a Photo Manual to the site.

12. LABORATORY TESTS

12.1 Urine Pregnancy Tests

The UPTs will be performed at the study site, if the site is registered and conforms to CLIA regulations for such testing (possesses a current valid CLIA Certificate of Waiver), or at an appropriately registered reference laboratory. The investigator will report the UPT results on the eCRFs, in the subject's medical records, and in independent records maintained at the study site. The UPT used must have a minimum sensitivity of 25 mIU of β -hCG/mL.

13. END OF STUDY CRITERIA

At the end of each subject's participation in the study, the investigator will complete an EOS Disposition form for all completed and discontinued subjects.

13.1 Completion of the Study

Subjects who complete the 12-week course of treatment as specified in this protocol will be considered to have completed the study.

13.2 Subject Discontinuation

A subject may be withdrawn from the study prior to completion for any of the following reasons:

- AEs
- Death
- Lack of efficacy
- Lost to follow-up
- Non-compliance with test article
- Physician decision
- Pregnancy
- Progressive disease
- Protocol deviation
- Study terminated by Sponsor
- Withdrawal by subject; NOTE: if the subject decides to withdraw from the study due to an AE then it should be classified as withdrawal due to an AE
- Other (e.g., any reason that may affect the outcome of the study or safety of subjects)

If a randomized subject withdraws from the study prematurely for any reason, the site should make every effort to have the subject return to the clinic to perform all of the required visit activities and to collect and reconcile all test articles (if applicable). If the randomized subject will not return to the clinic, the site should make every attempt to contact the subject; otherwise the subject will be considered lost to follow-up.

When a subject is withdrawn from the study for a test article related AE (as defined in [Section 14.2](#)), when possible, the subject should be followed until resolution or stabilization of the AE. If the subject is discontinued from the study due to pregnancy, the pregnancy and its outcome should be followed.

Subjects who are prematurely withdrawn or discontinued from the study will not be replaced.

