17.3 Statistical Methods

All statistical processing will be performed using SAS® Version 9.4 unless otherwise stated.

The Safety population will include all randomized subjects who applied at least one dose of test article.

The mITT population will include all randomized subjects who applied at least one dose of test article.

The PP population will include all mITT subjects who met all I/E criteria, were compliant with the assigned test articles based on the subject diaries (applied at least 75% and no more than 125% of the expected test article applications for the specified duration of the study), did not miss the scheduled test article applications for more than 3 consecutive days (i.e., 3 consecutive days with no test article application), have no other evidence of material dosing noncompliance, and completed the primary endpoint evaluation at Week 12 within the designated visit window (Day 85 ± 4 days) with no protocol violations that would affect the treatment evaluation including use of the prohibited medications.

Subject randomization will be stratified by the number of non-inflammatory lesions (≤ 70 / > 70) present at the Baseline Visit in order to ensure balanced enrollment of subjects across the treatment groups by non-inflammatory lesion count. No subset analyses are planned based on baseline non-inflammatory lesion counts.

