17.3.2.3 Imputation of Missing Data

Subjects who are discontinued early from the study due to lack of treatment effect after 4 weeks of treatment will be included in the PP population analyses using LOCF. Subjects whose condition worsens and who require alternate or supplemental therapy for the treatment of their condition during the treatment phase of the study will be included in the mITT and PP population analyses using LOCF. Subjects discontinued early for other reasons will be excluded from the PP population, but included in the mITT population, using LOCF.

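### Section 13.2 lets sites end study visits for non-compliance or a protocol deviation, so the mITT vehicle comparison carries forward earlier counts where Week 12 counts could have been observed

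*Combined protocol and SAP*

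**What the plan says.** Section 13.2 (Subject Discontinuation) opens its list with "A subject may be withdrawn from the study prior to completion for any of the following reasons". Two of the entries are "Non-compliance with test article" and "Protocol deviation". Physician decision and an open-ended other category are also listed. No threshold is given for any of these.

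For a randomized subject who withdraws early, "the site should make every effort to have the subject return to the clinic to perform all of the required visit activities". Visit 5 serves as either the Week 12 or the early-termination visit. Under Section 9.4 lesion counts are taken there, and then "The subject will exit the study". No readable text asks for a later count at Week 12. Section 13.2 adds: "Subjects who are prematurely withdrawn or discontinued from the study will not be replaced".

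On the analysis side, Section 17.3 states: "The mITT population will include all randomized subjects who applied at least one dose of test article". Compliance and deviations do not affect membership. Section 17.3.2.1 makes the two vehicle comparisons in mITT with LOCF. Section 17.3.2.3, after dealing with lack of effect and with worsening that needs other therapy, states: "Subjects discontinued early for other reasons will be excluded from the PP population, but included in the mITT population, using LOCF". Section 17.3.2.4 plans no sensitivity analysis.

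**The concern.** The vehicle comparisons show that the study can separate active drug from vehicle. The mITT set is defined so that subjects who under-use test article, or who deviate from the protocol, still count in those comparisons. Section 13.2 lets a site end such a subject's visits. The subject stays in mITT, but a count from before Week 12 stands in for the Week 12 outcome. Unlike death, loss to follow-up or withdrawn consent, this missingness is created by the protocol: the subject may have been willing to attend.

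About 50 sites would use this discretion without a common threshold. If its use differed between arms, the active-vehicle contrast would shift, and no planned analysis would show by how much.

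**Working it through.** **1. Does withdrawal serve any analysis?** The PP definition in Section 17.3 already removes subjects outside 75% to 125% of expected applications, those who break the consecutive-missed-days rule, and those with violations that would affect the treatment evaluation. Section 18.3 already requires every deviation to be documented. Under Section 17.3.2.3, early discontinuation for these reasons leads to PP exclusion anyway. Ending visits therefore gains the equivalence analysis nothing. A subject with a deviation too minor to meet the PP violation criterion could even be lost to PP through withdrawal.

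**2. Inputs from Section 17.1.** Reductions of 40% (reference), 38% (test) and 25% (vehicle); 462 mITT subjects per active arm and 231 on vehicle; two-sided alpha 0.05; power of at least 85%. The totals reproduce: 462 + 462 + 231 = 1155 and 346 × 2.5 = 865. The smaller planned contrast is test against vehicle, 38 − 25 = 13 points.

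**3. SD.** None is stated, so the power figure cannot be reproduced independently. Two values can be back-solved by normal approximation:
- Superiority: SE = SD × √(1/231 + 1/462) = SD × 0.0806. Exactly 85% power at 13 points needs 13/SE = 1.96 + 1.036, so SD ≈ 53.8.
- Equivalence: two one-sided tests on the ratio, 346 per arm, 38 against 40, limits 0.8 and 1.25 as in Section 17.3.2.1. Power of 85% needs SD ≈ 32.3. At that SD, superiority power is 99.9%, which fits the plan's wording of at least 85%.

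**4. Effect of carrying counts forward.** Let w be the share of an arm withdrawn before Week 12 and f the share of the Week 12 reduction present in the carried count. Then arm mean = Week 12 mean × [1 − w(1 − f)]. Both w and f are assumptions, and the SD is held fixed. Power = Φ(D/SE − 1.96).

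| Withdrawn | f | Test − vehicle, D | Power, SD 32.3 | Power, SD 53.8 |
|---|---|---|---|---|
| none | – | 13.0 | 99.9% | 85.0% |
| 5% all arms | 0.5 | 12.7 | 99.8% | 83.2% |
| 10% all arms | 0.5 | 12.35 | 99.7% | 81.3% |
| 20% all arms | 0.5 | 11.7 | 99.4% | 77.0% |
| 20% all arms | 0 | 10.4 | 97.9% | 67.0% |
| active 15%, vehicle 5% | 0.5 | 10.8 | 98.5% | 70.0% |
| active 5%, vehicle 15% | 0.5 | 13.9 | above 99.9% | 89.5% |

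Example for the sixth row: 38 × (1 − 0.15 × 0.5) − 25 × (1 − 0.05 × 0.5) = 35.15 − 24.375 = 10.8.

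**5. No true effect.** With a 25% reduction in both arms, withdrawal of 5% on active and 15% on vehicle, and f = 0.5, the spurious difference is 25 × (0.975 − 0.925) = 1.25 points. The two-sided rejection rate rises from 5% to 7.7% (SD 32.3) or 6.0% (SD 53.8).

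**6. The right comparator.** The 13.0-point row assumes that retained subjects respond in full. Subjects who under-use test article may not. If 10% of each arm kept only half of the active-vehicle benefit, observed Week 12 counts would give 0.9 × 13 + 0.1 × 6.5 = 12.35, the same as the LOCF figure at 10%. The gain from retention is therefore an observed outcome in place of an assumed one, not a reliably larger difference.

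**The case against.** The strongest reply is that the list reads as a set of disposition codes. It also contains death, loss to follow-up and sponsor termination, and Section 13 calls for an end-of-study disposition form. The verb is permissive. The written response to non-compliance is to carry on: footnote 7 of the Schedule of Events calls for re-education, and Section 9.3 has application demonstrated again if needed and the subject reminded to continue. This stands as far as expected practice goes. A reader might infer that a site would routinely exit a subject over missed diary days, and the documents do not support that. The sentence still grants authority to withdraw, and if only coding was meant, a clarification costs nothing.

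A reader might also take the gap between 1155 mITT and 865 PP (290, or 25.1%) as the share at risk. It is not a withdrawal rate. The 865 comes from 346 × 2.5, and PP exclusion also covers subjects who complete all visits but are non-compliant, outside the Week 12 window or using prohibited medication.

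The early-termination visit does provide a count, so the carried value need not be an old scheduled one. Unless that visit falls within Day 85 ± 4, it is still not a Week 12 outcome.

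Differential withdrawal by arm is conjecture in a double-blind study; it is possible, but not shown. Finally, Appendix 3 has parts on dose modifications and on documenting compliance whose content was not readable in the copy reviewed, and it may bear on this.

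**Conclusion.** The point holds as one of avoidable missing data. The plan permits study withdrawal for two reasons that need not end follow-up, seeks no Week 12 count afterwards, and fills the mITT vehicle comparison by LOCF with no sensitivity analysis.

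Its size cannot be fixed from the documents, because neither the number withdrawn for these reasons nor the timing is given. With equal withdrawal of 5% to 20% and half the reduction present, the 13-point difference would shrink by 0.3 to 1.3 points. A 15% against 5% imbalance would move it to 10.8 or 13.9, depending on direction.

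Two stronger readings are tempting. One is that the vehicle comparison loses its planned power. At the SD implied by the equivalence calculation, power stays above 97% in every row of the table; only if the true SD were near 53.8 would the loss matter. The other is that the rule favours one side. LOCF could bias the contrast either way, and the documents give no basis for a direction. This is a worthwhile, inexpensive improvement and does not threaten the study's validity.

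**What to change.** Change data collection only:

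- In Section 13.2, state that non-compliance with test article or a protocol deviation is not by itself a reason to end study visits, including under the physician-decision and other categories. Without that last clause the same subjects could be withdrawn under another label.
- Ask such subjects to attend the remaining scheduled lesion-count visits through Week 12, unless they withdraw consent or are withdrawn for a safety or other clinical reason as now.
- In Section 17.3.2.3, state that their observed Week 12 count is used in mITT. This is worth saying because Section 13.1 defines study completion by the 12-week course of treatment.
- Leave the PP criteria unchanged, and leave unchanged the LOCF rule for subjects whose condition worsens and who need alternate or supplemental therapy.

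The cost is a wording amendment and a few extra attendances at visits already in the schedule. Some mITT counts will come from subjects who under-used test article, which the mITT definition already intends.
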